9.1.2. Index Date

The date of the first dispensing or administration of ritlecitinib during the study period will be the index date.

9.2. Setting

Denmark, France, and Sweden have universal healthcare, whereby routinely collected data continuously accrue in the participating nationwide databases (described in Section 9.4). The use of the three population-based data sources will contribute to generalisability of the study results to AA patients in the EU. Data sources have been selected given adequate capture of some or all key study variables and relatively large underlying population sizes of patients across the regions. Indeed, the Danish, French, and Swedish databases capture information from nearly the entire populations of their residents. These large real-world data sources are assumed to be representative of patient and physician populations in their respective countries and will provide invaluable data to evaluate measurable indicators of HCP's adherence to the RMMs.

9.2.1. Inclusion Criteria

Patients must meet all of the following inclusion criteria to be eligible for inclusion in the study:

- 1. Have at least one dispensing of ritlecitinib during the study period
- 2. Have at least 12 months of continuous history in a participating data source before the index date

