9.1.1. Study Population and Study Period

The study population will include patients identified in each data source with a record of treatment with ritlecitinib during the study period. The study period will be 5 years following product launch: from 15 September 2023 through 14 September 2028.

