9.3.1. Exposure

The date of the first dispensing of ritlecitinib during the study period will be the index date. The exposure will continue until the end of a 90-day grace period following the estimated discontinuation of the index treatment. Duration of each dispensing will be computed based on days supplied, estimated based on assumed daily dose, package size, and number of packages in each dispensing. Only the first continuous treatment episode will be considered in this study.

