9.3.7. Preliminary Operational Definitions of the Main Study Variables

Generally, in the participating data sources, disease is identified by diagnoses recorded at hospitalizations (all three countries) or at hospital-based specialist outpatient clinics (Denmark and Sweden). Diagnoses are currently coded using the World Health Organization (WHO) International Classification of Diseases, Tenth Revision (ICD-10). The Danish version of the ICD-10 may have more detailed codes compared with the WHO ICD-10. ICD-11 will be used if introduced during the study period. Treatment records originate, depending on the database, from outpatient dispensings, from hospital administrations, and are coded using the Anatomical Therapeutic Chemical (ATC) classification or local structured vocabularies (e.g., local treatment codes in Denmark). Ritlecitinib and concomitant medications and vaccinations will be identified using ATC codes or hospital treatment codes as appropriate. Data on laboratory tests, available from Denmark and France, will be identified using Nomenclature, Properties and Units (NPU) codes or local codes as appropriate. Surgeries will be defined using country-specific procedure/surgery codes. Age (date of birth) and sex will be used as reported in the databases.

Table 1 summarizes the initial operational definitions and data availability per data source, of the eligibility criteria, the exposure and the endpoints. The refined, country-specific definitions of all study variables as well as the final list of other variables with their operational definitions will be provided in the Statistical Analysis Plan (SAP).

Table 1. Preliminary Definitions of the Main Study Variables

Measure	Availability and initial operational definition			
	Denmark France		Sweden	
Ritlecitinib initiation	ATC code L04AF08			
Indicators of Adherence to	RMMs			
Lab: lymphocyte count	Potential candidate example codes (subject to refinement): NPU codes NPU02902 B— Neutrophilocytes; NPU02636 B— Lymphocytes; num.c.	Complete blood count including platelets: TNB code 1104	Not available	
Lab: platelet count	NPU03568 B— Thrombocytes	Complete blood count including platelets: TNB code 1104	Not available	
Screening for TB	Not available	In/outpatient lab test (no results)	Not available	
Screening for viral hepatitis B or C	Not available	In/outpatient lab test (no results)	Not available	

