9.4. Data Sources

9.4.1. Denmark

Denmark's population-based registers, linkable by a unique identifier, the central person registration (CPR) number, assigned by the CRP registry to all residents at birth or upon immigration contain routinely collected data for the country's entire population of more than 5.8 million individuals and allow long-term follow-up of individuals for assessment of safety events such as MACE or malignancy (15, 16). The CPR registry contains information on age, sex, migrations and deaths. The Danish National Prescription Registry (DNPR) contains information on all prescription medicines dispensed at Danish community pharmacies with

PFIZER CONFIDENTIAL

products recorded via Anatomical Therapeutic Chemical (ATC) codes. Certain drugs administered at specialist hospital-based clinics are captured in the Danish National Patient Register (NPR), and tentatively from 2024, in the Danish Hospital Medicines Register (currently in development and expected to become complete in 2024 (17)). Newly approved drugs, especially expensive treatments, are often first prescribed or administered at the specialist hospital clinics with follow-up with general practitioners. Such treatments (active substance) may be identifiable via treatment codes in the Danish NPR. The Danish NPR records diagnoses (WHO ICD-10/ICD-11 codes) and procedures (NOMESCO codes) during inpatient or outpatient hospital encounters. The Danish Cause of Death Registry records causes of death using ICD-10 code categories. The Danish Health Services Register may be used to ascertain referrals for hearing-loss related procedures as well as administration of reimbursed vaccinations; identification of pregnancy referrals may also be explored. The Danish Laboratory Research Database contains information about laboratory tests and their results from hospital-based laboratories. The Danish Vaccination Registry may be used to obtain data on vaccinations (18). Most of these databases have been used extensively in pharmacovigilance, and multiple algorithms have been validated (19-27).

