9.9. Limitations of the Research Methods

The limitations of the study are included below:

- While ritlecitinib is expected to be well-captured in outpatient dispensing streams, the Swedish national health registers have minimal capture of inpatient hospital administrations and dispensings, and partial capture of outpatient hospital administrations (i.e., medications administered in outpatient clinics located in hospitals) and dispensings. Similarly, in the SNDS, hospital admissions only capture administered medications that are expensive. Thus, most medications that are dispensed or administered primarily through hospital channels will be missed. As ritlecitinib is mainly expected to be dispensed in outpatient settings, this limitation is unlikely to result in a large proportion of missed exposed patients.
- Given the use of data sources from three distinct European countries, there will be variability in capture of indicators of adherence to the RMMs across the data sources. For example, data on laboratory tests and vaccinations are not available in Sweden and may be under recorded in Denmark and France. In France, only reimbursed vaccinations are recorded, meaning some vaccines (e.g., yellow fever vaccination) will be missed. All major variabilities in data elements across data sources will be described in the SAP.
- Other limitations, which are similar across many administrative data sources, include incomplete identification of ongoing pregnancies and pregnancies ending in a

termination (as they are identifiable only by pregnancy end date); underascertainment of lifestyle factors such as smoking status and smoking history; and challenges in identifying screening for TB and hepatitis B and C in all participating countries.

- While the study includes databases from multiple regions within the EU that have adequate data quality, results from the participating countries may not necessarily be generalizable to other countries in the EU.

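### Inclusion and exposure (9.2.1, 9.3.1) rest on a dispensing, while the population and index date (9.1.1, 9.1.2) also admit an administration; captured hospital starters may be excluded or, if 9.3.1 governs, indexed late

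*Protocol*

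**What the plan says.** Four sections of the protocol define who enters and when time zero falls.

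- **9.1.1 (population):** patients "with a record of treatment with ritlecitinib during the study period".
- **9.1.2 (index date):** "The date of the first dispensing or administration of ritlecitinib during the study period will be the index date".
- **9.2.1 (inclusion criterion 1):** "Have at least one dispensing of ritlecitinib during the study period".
- **9.3.1 (exposure):** "The date of the first dispensing of ritlecitinib during the study period will be the index date". Duration is then built from the days supplied by each dispensing. No rule is given for an administration.

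Other sections bear on how to read these:

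- **9.3.7** treats the two record types as distinct: "Treatment records originate, depending on the database, from outpatient dispensings, from hospital administrations". It says ritlecitinib will be found by ATC code or hospital treatment code as appropriate. The initiation row of Table 1 shows only the ATC code, and the table is described as initial.
- **9.4.1 (Denmark):** "Newly approved drugs, especially expensive treatments, are often first prescribed or administered at the specialist hospital clinics with follow-up with general practitioners". It adds that such treatments may be identifiable through treatment codes in the patient register.
- **9.9** acknowledges incomplete hospital capture in Sweden and France and expects few missed patients: "As ritlecitinib is mainly expected to be dispensed in outpatient settings".
- **9.7** counts the laboratory and pre-treatment vaccine windows from the index date: 3 months before for baseline tests, week 4 ± 2 weeks after for monitoring, and 4 weeks before for live vaccines.

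**The concern.** 9.1.2 and 9.3.1 each claim to set the index date, and they set it differently. Criterion 1 is narrower than the population in 9.1.1. A programmer working from 9.2.1 and 9.3.1 would discard hospital administration records that 9.1.2 and 9.3.7 say to use.

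Two consequences are possible, and they arise under different conditions.

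1. **Exclusion.** A patient whose only captured records are administrations fails criterion 1, whichever index date is used.
2. **Late index.** A patient with a captured administration and a later dispensing is dated correctly under 9.1.2 and late under 9.3.1. Early treatment time is then treated as pre-treatment time.

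The second could lower apparent monitoring adherence and raise apparent baseline screening in the same patient. Denmark is where it is most plausible. 9.4.1 describes a hospital-first, community-later pattern there for new drugs, and Denmark is one of two countries with laboratory data and the only one with results.

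**Working it through.** **Reproducing the plan's own figure.** Section 9.5 uses n = P(1−P)Z²/e². With P = 0.50, Z = 1.96 and e = 0.05 (half of a 10-point width), n = 0.25 × 3.8415 / 0.0025 = 384.1, rounded up to 385. This matches Table 2. The point here does not dispute that figure; it is used only as a yardstick.

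**Inputs from the protocol.** Monitoring window: week 4 ± 2 weeks, so days 14 to 42, which is 29 days. Vaccine window: 28 days before index. Baseline window: 3 months before index, taken as 90 days.

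**Inputs not in the protocol.** The gap d in days from first administration to first dispensing, and the share f of patients affected. Both are varied below as assumptions.

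**Step 1: shift of the windows if 9.3.1 is applied.** Counted from true start, the monitoring window runs from d+14 to d+42. Its overlap with days 14 to 42 is 29 − d days, and zero from d = 29. The vaccine window overlaps the intended one by 28 − d days, and the baseline window by 90 − d days.

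| d | Monitoring overlap (of 29) | Vaccine overlap (of 28) | Baseline overlap (of 90) |
|---|---|---|---|
| 0 | 29 | 28 | 90 |
| 7 | 22 | 21 | 83 |
| 14 | 15 | 14 | 76 |
| 21 | 8 | 7 | 69 |
| 28 | 1 | 0 | 62 |
| 29 | 0 | 0 | 61 |
| 60 | 0 | 0 | 30 |
| 90 | 0 | 0 | 0 |

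**Step 2: a monitoring test done on day 28 of treatment.** It is counted only if d + 14 ≤ 28, so it is missed once d > 14. It falls before the assigned index date once d > 28. It then lies within the 90-day baseline window as long as d − 90 ≤ 28, that is up to d = 118, and is counted as pre-initiation screening.

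**Step 3: illustrative effect on a monitoring proportion.** Suppose every test is on day 28, a share f has d > 14, and those patients have no other test in the shifted window. The observed proportion is then P(1 − f). With a true P of 75%:

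- f = 5%: 71.3% (3.75 points low)
- f = 10%: 67.5% (7.5 points low)
- f = 20%: 60.0% (15 points low)

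The 95% CI half-width at P = 75% and n = 385 is 1.96 × √(0.75 × 0.25 / 385) = 4.3 points. The bias passes that once f exceeds 4.3/75, about 5.8%. Repeat testing would make the bias smaller.

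**Step 4: illustrative effect of excluding administration-only patients.** If a share f of 385 is excluded, 385(1 − f) remain. The CI width at P = 50% is 2 × 1.96 × √(0.25/n):

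- f = 5%: n = 366, width 10.2 points
- f = 10%: n = 346, width 10.5 points
- f = 20%: n = 308, width 11.2 points

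The precision loss is slight. The larger issue is that these patients belong to the population in 9.1.1 and would not be described at all.

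**The case against.** The strongest reply is that this is loose wording with little consequence. Several parts of that reply stand.

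- **Hospital codes are already planned.** A reader might infer from Table 1 that hospital treatment codes will be ignored. The text of 9.3.7 allows them, calls the table initial and leaves refined definitions to the SAP. The table row needs aligning; it is not evidence of a separate gap.
- **A dispensing need not be a community dispensing.** 9.9 applies the word to hospital settings too. A pack handed out at a hospital clinic could meet criterion 1, so only records that count strictly as administrations are affected.
- **9.4.1 speaks of drugs first prescribed or administered at clinics.** A drug prescribed there may be dispensed at a community pharmacy and captured in the prescription registry. The sentence is about new drugs in general. The statement specific to ritlecitinib is in 9.9, and the two are compatible.
- **Mis-dating is conditional.** A reader might infer that the windows are shifted as the plan stands. They shift only if 9.3.1 prevails over 9.1.2.
- **The reach is limited.** In Denmark, TB and hepatitis screening are unavailable, so among the laboratory and vaccine indicators only lymphocyte count, platelet count and live vaccines could move. Sweden has neither laboratory nor vaccine data. Administrations that are not captured at all are a separate limitation, already acknowledged in 9.9 for Sweden and France.

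The reply does not remove the contradiction. 9.9 does not discuss captured hospital records that a dispensing rule would discard. The freedom in 9.7 to revise windows does not extend to the index date or inclusion rule. The SAP may refine definitions, but it cannot follow two index dates at once.

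**Conclusion.** The contradiction is established by the text: 9.1.1 and 9.1.2 against 9.2.1 and 9.3.1. Exclusion of captured administration-only patients follows from criterion 1 under either index date. Late indexing follows only if 9.3.1 is applied, and then the thresholds are exact: a day-28 test is lost beyond a 14-day gap and counted as baseline beyond a 28-day gap.

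The overall size is unknown. The documents give no share of hospital starters and no gap, and 9.9 points to a small share. A reader might infer that a large fraction of Danish users is affected; nothing in the protocol supports any particular fraction. The values of f in the working are illustrations only, and those for monitoring also assume that all tests fall on day 28 with no repeats. They show that a share a little under 6% with d > 14 could outweigh sampling error at n = 385, not that it will.

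This is a definitional inconsistency that should be corrected before extraction, not a demonstrated bias.

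**What to change.** Use one rule in 9.1.1, 9.1.2, 9.2.1 and 9.3.1: *first recorded dispensing or captured hospital administration/treatment code*. Then:

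- align the initiation row of Table 1 with the 9.3.7 text that already allows hospital treatment codes;
- state in 9.3.1 how exposure duration is computed when the record is an administration;
- report, by country, how many patients are indexed from each type of record.

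A sensitivity analysis restricted to patients whose first record comes from a fully captured source is optional.

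The cost is a handful of wording edits and one extra descriptive count. The Danish sources are already listed in 9.4.1, although the hospital medicines register was still in development when the protocol was written. The one real downside is that hospital records need an explicit days-supply assumption. Extraction is planned to start in September 2027, so there is time to make the change.

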9.2.2. Exclusion Criteria

There are no exclusion criteria for this study.

9.3. Variables

Variables will include patient demographics (age and sex), comorbidities (measured by diagnoses from specialist health care at hospital encounters or treatment proxies), medication dispensings, procedures, and laboratory tests (Denmark and France only) prior to initiating ritlecitinib and monitoring tests during follow-up after treatment initiation. The maximum

lookback period for ascertaining characteristics before ritlecitinib initiation will be 12 months (365 days), but will vary for a given RMM measure, per SmPC.

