9.3.3. Risk Factors for Thromboembolic Events

Risk factors for thromboembolic events will be identified during the 12 months prior to and including index date:

- Age >65 years
- History of VTE
- History of arterial thromboembolism (ATE)
- Major surgery within 90 days before the index date
- Combined hormonal contraceptives
- Hormone replacement therapy
- Pregnancy
- Malignancy
- CVD

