9.3.4. Risk Factors for Malignancy

Risk factors for malignancy will be identified during the 12 months prior to and including index date:

- Age >65 years
- History of malignancy
- History of NMSC
- Obesity
- Alcohol-related conditions
- Tobacco-related conditions

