	ICD-10-CM codes to ICD-10 equivalents whenever feasible)			

Table 1. Preliminary Definitions of the Main Study Variables

Risk factors for thromboe	mbolic events, malignancy or C	CVD			
Age 65 years or older	per date of birth				
History of thromboembolic events including VTE or ATE	ICD-10 codes I26, I260A I269 I82.2; I82.3, I82.8, I82.9 O22.3 Denmark only: O882D, O882E	3, O87.0, O87.1	, I81, I82.0,		
Malignancy (any, primary or secondary)	ICD-10 codes chapter C	ICD-10 codes chapter C, treatment codes if relevant	ICD-10 codes chapter C		
Major surgery within 90 days of index date	NOMESCO Classification of Operations on the nervous system: KA; Operations on endocrine organs: KB; Operations on the heart and large intrathoracic vessels: KF; Operations on respiratory organs, chest, mediastinum and diaphragm: KG; Breast surgeries: KH; Operations on digestive organs and spleen: KJ; Operations on the urinary tract, male genitalia and retroperitoneal tissue: KK; Operations on female genitalia: KL; Obstetric operations: KM; Operations on the musculoskeletal system: KN	CCAM codes for major surgery	•		
Combined hormonal contraceptives	ATC codes G03A		Not available (not reimbursed)		
Hormone replacement therapy	AT	C codes G03			
Obesity	ICD-10 codes E65				
Alcohol-related conditions	ICD-10 codes K70, F10				
Tobacco-use related conditions	ICD-1	0 codes J40-J47			
Diabetes	ICD-10 codes F	E10-E14, ATC codes A10	1		

Table 1. Preliminary Definitions of the Main Study Variables

Hypertension	ICD-10 codes I10-I15, treatment proxies			
Hyperlipidaemia	ICD-10 codes E78, treatment p	proxies, laboratory data (l	Denmark only)	
Coronary artery disease	ICD-10 codes I21-I25 Nordic Medico-Statistical Committee (NOMESCO) codes for coronary artery bypass graft (CABG) or percutaneous intervention (PCI): FNF, FNG, FNA, FNB, FNC, FND, FNE	ICD-10 codes I21-I25	ICD-10 codes I21-I25 Nordic Medico- Statistical Committee (NOMESCO) codes for coronary artery bypass graft (CABG) or percutaneous intervention (PCI): FNF, FNG, FNA, FNB, FNC, FND, FNE	
Chronic kidney disease	ICD-10 codes N18, potentially dialysis procedure codes	ICD-10 codes N18	ICD-10 codes N18, potentially dialysis procedure codes	
AA diagnosis	ICD	0-10 code L63		

Source of ICD-10 codes: Denmark and Sweden, inpatient (hospital) or outpatient (specialist visits); France, inpatient hospital encounters. ICD-10 codes with trailing letters are applicable in Denmark only.

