9.4.2. France

The French nationwide administrative database (Système National des Données de Santé – SNDS; French Administrative Healthcare Database) covers more than 99% of the French population – near 67 million inhabitants – from birth (or immigration) to death (or emigration), even if a subject moves, changes occupation or retires (28, 29). Using a unique pseudonymized identifier, it merges all reimbursed outpatient claims from all French healthcare insurance schemes with hospital-discharge summaries from public and private hospitals, and the national death registry. Thus, all reimbursed medical and paramedical encounters are recorded. SNDS captures general characteristics (e.g., sex, year of birth, affiliation scheme, area of residence); registration for Long Term Disease with the diagnosis code, qualifying for full health insurance coverage; outpatient encounter details (e.g., medical and paramedical visits with practitioner specialty, medical and imaging procedures, laboratory tests, quantity of drugs dispensed, drug strength, medical devices; but no indication, physician prescription directions, drug posology or exam results); inpatient details (e.g., primary and associated hospital discharge diagnoses, procedures and laboratory tests performed, innovative or expensive drugs and medical devices invoiced in addition to the hospitalization, length of the hospital stay). Dates, associated costs, and prescriber and caregiver information are provided for each expenditure. Diagnoses are coded using ICD-10 codes. Drug dispensings are identified and captured through ATC codes, but also at the package level in outpatient settings with the Code Identifiant de Présentation (CIP; Presentation Identification Code), and at the unit of administration level in inpatient settings through the Unité Commune de Dispensation (UCD; Common Dispensing Unit). Procedures are coded according to the Classification Commune des Actes Médicaux (CCAM; Common Classification of Medical Procedures), and laboratory tests follow the Nomenclature des Actes de Biologie Médicale (NABM; Nomenclature of Medical Biology Acts). The SNDS database also includes the French National Death Register (CepiDC) data. Though neither medical indication nor result are recorded, the level of detail of the captured information enables an accurate characterization of patient healthcare journeys (30). SNDS has been used PFIZER CONFIDENTIAL

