9.7.1. Sensitivity Analyses

A sensitivity analysis will restrict to the subset of patients with an AA diagnosis on or up to 5 years before the index date.

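### Prior VTE, ATE, malignancy and NMSC are sought in at most 12 months of records, so Objective 2 history proportions and risk-factor counts are biased downward, and section 9.9 does not say so

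*Protocol*

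**What the plan says.** Section 9.3 fixes an upper limit: "lookback period for ascertaining characteristics before ritlecitinib initiation will be 12 months (365 days". The same sentence then lets the window differ between risk-minimisation measures. That exception concerns those measures, not the Objective 2 characteristics.

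Section 9.3.3 states: "Risk factors for thromboembolic events will be identified during the 12 months prior to and including index date". Its list includes history of VTE and of arterial thromboembolism. Section 9.3.4 states: "Risk factors for malignancy will be identified during the 12 months prior to and including index date". Its list includes "History of malignancy" and history of NMSC. Section 9.7, items 8 and 9, repeats 12 months for both groups.

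Three other places matter:

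- Section 9.2.1 requires at least 12 months of prior history. That is a minimum.
- Section 9.7.1 restricts its sensitivity analysis to patients with an "AA diagnosis on or up to 5 years before the index date".
- The Table 1 footnote (section 9.3.7) takes ICD-10 codes from inpatient and specialist outpatient contacts in Denmark and Sweden, but gives "France, inpatient hospital encounters" as the French source. For malignancy, the French column also allows treatment codes where relevant. Section 9.4.2 says the SNDS holds "registration for Long Term Disease with the diagnosis code", which Table 1 does not use.

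**The concern.** The label and the definition do not match. Having had an embolism or a cancer is a fact about a patient's past, but the plan looks for it only in the last year. Someone treated for cancer three years before index, with no cancer code since, is reported as having no such history.

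Objective 2 exists to describe which risk factors patients carry when they start ritlecitinib. Missing older events can only lower the proportions with a history and the number of risk factors per patient, so the error runs in the reassuring direction. More patients will not reduce it, and the planned 95% confidence intervals do not reflect it.

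In France the source restriction can add to the loss, because an event managed without an inpatient code is also missed. Results are presented separately by country, so the French figures may carry a larger downward bias than the Danish and Swedish ones, and a reader could take the gap for a real difference.

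**Working it through.** **The plan's own precision figures.** Section 9.5 uses n = P(1 − P)z²/e². For P = 0.50 and e = 0.05, 0.25 × 1.96² / 0.0025 = 384.1, rounded up to 385, as in Table 2. At P = 10% and n = 385, the 95% half-width is 1.96 × √(0.10 × 0.90 / 385) = 3.0 points, a width of 6.0 as in Table 3. These figures are sound, but they describe sampling error only.

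**What the window does.** The documents give no timing of past events and no re-coding rates, so the inputs below are assumptions:

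- T: past events are spread evenly over T years before index.
- r: yearly chance that an older event is coded again.
- L: look-back in years, no longer than T.

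Share captured: c(L) = L/T + (1 − L/T) × [1 − (1 − r)^L]. For L = 1 this is 1/T + (1 − 1/T) × r.

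With T = 5 and r = 0, c(1) = 1/5 = 20%. With T = 5 and r = 0.3, c(1) = 0.20 + 0.80 × 0.3 = 44%.

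| T (years) | r | Captured, 12 months | Captured, 5 years |
|---|---|---|---|
| 5 | 0 | 20% | 100% |
| 5 | 0.3 | 44% | 100% |
| 5 | 0.5 | 60% | 100% |
| 10 | 0 | 10% | 50% |
| 10 | 0.3 | 37% | 92% |
| 10 | 0.5 | 55% | 98% |
| 20 | 0 | 5% | 25% |
| 20 | 0.3 | 34% | 87% |
| 20 | 0.5 | 53% | 98% |

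The 100% entries for T = 5 follow by construction.

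**Set against the confidence interval.** Assume a true share with a history of 10%. The 12-month share is 10% × c(1), which runs from 0.5% (T = 20, r = 0) to 6.0% (T = 5, r = 0.5). The shortfall is 9.5 to 4.0 points, against a half-width of 3.0 points at P = 10% and n = 385.

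**France.** Assume further that inpatient codes show a fraction s = 0.5 to 0.7 of such events. The observed share becomes 10% × c(1) × s, from 0.5% × 0.5 = 0.25% to 6.0% × 0.7 = 4.2%. Treatment codes would recover some malignancies.

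**Whether a longer window is available.** Section 9.2.1 sets a floor on prior history, not a ceiling. Section 9.4.2 describes SNDS coverage from birth or immigration to death or emigration. Section 9.4.3 dates the Swedish drug register from July 2005. Section 9.4.1 says the Danish registers allow long-term follow-up. Section 9.7.1 already plans a 5-year look-back for one diagnosis. The protocol gives no reason for capping the history items at 12 months.

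**Whether it is disclosed.** Section 9.9 mentions under-ascertained lifestyle factors and says only a subset of risk factors can be assessed. It names neither the short look-back nor the French inpatient source as a cause of missed history.

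**The case against.** The best defence is that a common 12-month window treats all patients and countries alike, and that 12 months is all the inclusion criteria guarantee. Items 8 and 9 state the window openly, so nothing is presented as lifetime prevalence. This has weight: with all available records, look-back would differ between patients. Keeping the 12-month result as a sensitivity analysis preserves the benefit. It does not justify calling the main measure a history.

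Section 9.7 lets windows be revised, but to reflect local data flow. That does not commit anyone to a longer history for these items. The 12-month maximum is fixed in the protocol itself, so the point is not simply one left to the SAP.

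Table 1 is a different matter. Section 9.3.7 calls its definitions initial and defers refined country-specific ones to the SAP. The French source is therefore a secondary point, worth settling now but not a fixed error. A reader might infer that all four histories rest on inpatient codes alone in France; for malignancy that is wrong, since treatment codes are allowed.

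A reader might also infer that the 5-year look-back in section 9.7.1 contradicts the 12-month maximum. It does not strictly do so: one window defines a sensitivity subset, the other governs patient characteristics. It shows only that a longer look-back was considered workable.

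**Conclusion.** The point holds for the four history items: followed as written, the plan counts older events without a recent code as no history. The direction of the bias is certain wherever such events exist. Its size is not known. The 20% figure, and every range shown above, rests on assumed timing and re-coding, applied alike to four conditions that may differ.

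Three stronger readings are not supported:

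- That a stated fraction of prior events, such as half or more, will be missed. No input for such a figure stands in the documents.
- That the share of high-risk patients is understated. The protocol defines no high-risk class. The effect falls on the individual history proportions and the risk-factor counts. Age and current-medication factors are untouched, and the adherence indicators of Objective 1 do not depend on these items.
- That the French alopecia areata subset could be repaired with Long Term Disease codes or the prescriber's specialty. The documents do not say that alopecia areata qualifies for such registration, and a prescriber's specialty is not a diagnosis. What can be said is that, under the Table 1 footnote, this subset rests on inpatient L63 codes.

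**What to change.** 1. For history of VTE, ATE, malignancy and NMSC, use a fixed longer look-back (for example 5 years, in line with section 9.7.1) or all available records. Change sections 9.3, 9.3.3, 9.3.4 and 9.7 (items 8 and 9) together.
2. Report the 12-month version as a sensitivity analysis. Keep 12 months for medications and 90 days for surgery.
3. In the French column of Table 1, add Long Term Disease diagnosis codes to the inpatient codes for these items.
4. If the window is not lengthened, relabel the items as recorded in the prior 12 months and state the downward bias in section 9.9.
5. In either case, note in section 9.9 that the French alopecia areata subset rests on inpatient L63 codes.

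The cost is a longer extraction from sources already in use. Patients with only the required 12 months of records will have a shorter look-back than others, which the 12-month sensitivity analysis addresses. Items 4 and 5 need only text.
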